1.8 Nonclinical Experience with Study Medications

1.8.1 CTAP101 Capsules

To study the toxicity of CTAP101 Capsules, an earlier formulation of CTAP101 Capsules was administered to dogs for 3 months and resulted in typical vitamin D-induced toxicities including hypercalcemia, hypercalciuria, soft tissue mineralization (e.g., kidney, stomach, aorta and heart) and death. Severe adverse reactions to CTAP101 Capsules were observed in dogs treated with 500 or 1,000 mcg/day and were associated with serum calcifediol levels >450 ng/mL following 1 month of treatment.

Using the current formulation of CTAP101 Capsules, dogs were treated daily for three months with doses up to 45 μ g (~4.5 mcg/kg/day). No signs of toxicity were observed at the highest dose tested which was associated with serum calcifediol levels >150 ng/mL.

Calcifediol administration (orally through addition to the diet) to rats for 6 months has been reported to produce signs of toxicity at daily doses >40 mcg/kg. Toxicities included an increased incidence of nephrocalcinosis and uroliths. Oral administration of calcifediol to dogs at ≤ 2 mcg/kg/day resulted in no compound-related findings.

Results from in vitro drug release and nonclinical PK studies in male Yucatan swine demonstrate that CTAP101 Capsules have an ER profile. In swine, the bioavailability (BA) of calcifediol following the administration of CTAP101 Capsules was approximately 30% lower than that from an IR capsule preparation. Further, a delay in the release of the active ingredient (time of maximum concentration or $t_{max} > 7$ hours) was observed as compared to the IR formulation ($t_{max} \sim 4$ hours).

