1.9 Previous Clinical Experience with CTAP101

CTAP101 Capsules (30 mcg) have been approved as Rayaldee® by the US Food and Drug Administration (FDA) for the treatment of SHPT in adults with stage 3 or 4 CKD and VDI,

defined as serum total 25-hydroxyvitamin D levels less than 30 ng/mL. The clinical studies which supported FDA approval are described below.

There have been three previous single-dose phase 1 studies with CTAP101 Capsules ([CTAP101-CL-1005](#), [CTAP101-CL-1011](#) and [CTAP101-CL-1016](#)), two phase 2 studies, of which one was a single-dose study ([CTAP101-CL-2004](#)) and one was a repeat-dose study ([CTAP101-CL-2008](#)), and three phase 3 studies ([CTAP101-CL-3001](#), [CTAP101-CL-3002](#) and [CTAP101-CL-3003](#)). Studies CTAP101-CL-1011, CTAP-CL-1016 and CTAP101-CL-2008 were conducted with the current formulation of CTAP101 Capsules (30 mcg per capsule). Two of the phase 3 studies (CTAP101-CL-3001 and CTAP101-CL-3002) were identical double-blind, placebo-controlled pivotal trials and the third (CTAP101-CL-3003) was a follow-on open-label extension trial.

The single-dose studies confirmed the ER characteristics of the investigational drug product and that the current formulation has a BA of approximately 25% when administered in the fasting state. Administration of a single pharmacologic dose of CTAP101 Capsules following a high-fat, high calorie meal resulted in a significantly higher exposure of calcifediol compared to when administered in a fasted state. An approximate 5-fold increase in maximum serum concentration (C_{max}) and a 3.5-fold increase in area under the concentration curve (AUC) was observed in the fed group compared to the fasted group (CTAP101-CL-1016).

In CTAP101-CL-2008, a double-blind, placebo-controlled, randomized repeat-dose study, daily administration of CTAP101 Capsules increased serum total 25-hydroxyvitamin D levels to ≥ 30 ng/mL in nearly all subjects and decreased mean plasma iPTH from pre-treatment baseline (BL) and compared to placebo during 6 weeks of treatment. The mean % decrease in iPTH from BL in the per-protocol (PP) population was related to the administered dose: -20.9, -32.8, and -39.3 for the 30, 60 and 90 mcg groups, respectively.

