5.5.2 Diet Restrictions

There are no study specific dietary restrictions. Subjects should follow their dietary plan if one has been prescribed. Changes in prescribed dietary phosphorus or calcium therapy are discouraged and any changes during the study should be captured in the electronic case report form (eCRF).

Subjects will maintain a dietary intake during the study of approximately 1,000-1,500 mg per day of elemental calcium per dietary counseling and, as necessary, administration of a daily calcium supplement. Subjects will complete a dietary questionnaire on Visit 1 and receive counseling from a dietitian on their dietary calcium intakes, if needed.

Subjects will report to the phase 1 unit on the mornings of Day 1 and Day 29 after an overnight fast. They will receive standardized meals while housed in the phase 1 unit. These meals will contain 400 mg of elemental calcium and will be administered at approximately 2, 6, and 10 hours post-dose.

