5.2 Pharmacokinetic properties

Absorption

Calcifediol or 25-hydroxycholecalciferol, such as vitamin D analogues, is absorbed in the intestine if the absorption of fats is normal, through the chylomicrons, principally in the middle sections of the small intestine; approximately 75–80% is absorbed this way.

Distribution

Calcifediol is the main circulating form of vitamin D. The serum concentrations of 25(OH)-cholecalciferol reflect the organism's vitamin D reserves which are usually between 25 and 40 ng/mL (62.5 to 100 nmol/L) in healthy individuals. Following the oral administration of calcifediol, the time in which the maximum serum concentration is reached is approximately 4 hours. Its half-life is around 18 to 21 days and its storage in the adipose tissue is less significant than that of vitamin D, due to its lower liposolubility; calcifediol is stored in the adipose and muscle tissue for extended periods of time. The pharmaceutical form of soft capsules offers a 22% higher bioavailability than the pharmaceutical form of an oral solution in vials. This difference is not considered clinically significant given that the dose must be determined on an individual basis depending on the serum levels of 25-OH-cholecalciferol and calcium, and these levels must be controlled during the treatment.

Metabolism or Biotransformation

Elimination

Calcifediol is principally excreted in the bile.

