5.2 Pharmacokinetic properties

Vitamin D

Sun exposure: UVB light converts 7-dehydrocholesterol, found in the skin, to colecalciferol.

Absorption: Vitamin D is easily absorbed in the small intestine. Food intake potentially increases the absorption of vitamin D.

Distribution and biotransformation: Colecalciferol and its metabolites circulate in the blood bound to a specific globulin. Colecalciferol is converted in the liver by hydroxylation to 25-hydroxycholecalciferol. It is then further converted in the kidneys to 1,25-dihydroxycholecalciferol. 1,25-dihydroxycholecalciferol is the active metabolite responsible for increasing calcium absorption. Vitamin D, which is not metabolised, is stored in adipose and muscle tissues.

After a single oral dose of colecalciferol, the maximum serum concentrations of the primary storage form are reached after approximately 7 days. 25(OH)D₃ is then slowly eliminated with an apparent half-life in serum of about 50 days. Colecalciferol and its metabolites are excreted mainly in the bile and faeces.

Elimination: Vitamin D is excreted mainly in bile and faeces with a small percentage found in urine.

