### 7.3 Statistical Analysis of Pharmacokinetic Parameters

As an exploratory analysis, PK parameters for observed and BL-adjusted serum calcifediol will be compared between treatments using a mixed-effects model for the PK population. The dependent variable will be the value of the PK parameter. The model will include a term for treatment and BL calcifediol as a covariate. The PK parameters

compared may include  $C_{max}$  and  $AUC_{0-24h}$  for Day 1 and  $C_{max}$ ,  $AUC_{0-24h}$  (ie,  $AUC_{tau}$  for daily dosing regimen), and  $C_{avg}$  for Day 29. Additional parameters (eg, alternative  $AUC_{0-t}$  parameters) may be compared (and/or substituted) as deemed appropriate.

[figure not shown]
Treatment least-squares means and least-squares differences and 95% confidence intervals for the difference will be constructed for the values of each parameter. In addition, the  $P$  values will be presented for treatment and BL in the analysis table.

The SAS Proc Mixed code is as follows:

[figure not shown]
```
PROC MIXED DATA = adpc;
  BY paramn paramcd param;
  CLASS trtp;
  MODEL aval = trtp base_calcifediol;
  ESTIMATE 'CTAP101 Capsules vs. Calcifediol IR' trtp 1 -1 0 0 / cl;
  ESTIMATE 'CTAP101 Capsules vs. Cholecalciferol' trtp 1 0 -1 0 / cl;
  ESTIMATE 'CTAP101 Capsules vs. Paracalcitol plus cholecalciferol' trtp 1 0 0 -1 / cl;
  RUN;
```

[figure not shown]
Alternative statistical analyses may be provided if insufficient data or issues with the model are found.

CCI

CCI

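### The exploratory PK comparison in SAP 7.3 is labelled mixed-effects but is an ANCOVA with one pooled residual variance, so its 95% intervals may be too narrow or too wide, depending on how the arm variances differ

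*SAP*

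**What the plan says.** SAP 7.3 says that PK parameters for observed and baseline-adjusted serum calcifediol "will be compared between treatments using a mixed-effects model for the PK population". The text names two terms, treatment and baseline calcifediol, and takes the parameter value itself as the response, with no transformation. The PROC MIXED code matches that text: "MODEL aval = trtp base_calcifediol", fitted separately for each parameter through BY, with three ESTIMATE statements that set CTAP101 against each other arm. The code has no RANDOM statement, no REPEATED statement and no GROUP= option. Differences with 95% confidence intervals, and P values, are to be reported. Candidate parameters are Cmax and AUC0-24h on Day 1, and Cmax, AUC0-24h and Cavg on Day 29.

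The only safeguard in the section is that "Alternative statistical analyses may be provided if insufficient data or issues with the model are found". Protocol 9.8 describes the same comparison as exploratory, by simple summaries or ANOVA if feasible. SAP 3.1 plans about 20 subjects per arm. Neither document gives an arm-level SD for any PK parameter.

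**The concern.** There are two separate issues. The first is the name: a model with two fixed effects and one residual variance is an ANCOVA, whatever procedure fits it.

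The second is calibration. The residual variance is averaged over all four arms and then used for every pairwise contrast, although each contrast has sampling error from only two arms. The arms are a daily extended-release calcifediol dose, a 266 mcg immediate-release bolus, a 300,000 IU bolus of a precursor, and 800 IU of the precursor daily with paricalcitol. If the spread of calcifediol exposure differs among them, the reported intervals and P values are wrong by an amount that depends on the contrast. These are the only between-arm PK intervals visible in the two documents.

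**Working it through.** **Formula.** With n per arm, the pooled residual variance estimates the mean of the four arm variances, v̄. The code gives a contrast of arms i and j the variance 2v̄/n; the true variance is (v_i + v_j)/n. The small contribution of the covariate is ignored here. Hence

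model SE / true SE = √[2v̄ / (v_i + v_j)].

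The interval is too narrow when this is below 1, that is, when the two arms' average variance exceeds v̄. It is too wide when the ratio is above 1.

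**Worked example, SDs 1:2:1:1** (order CTAP101:IR:cholecalciferol:paricalcitol). v̄ = (1 + 4 + 1 + 1)/4 = 1.75. CTAP101 vs IR: √(3.5/5) = 0.84. The other two contrasts: √(3.5/2) = 1.32. Approximate coverage follows from 1.96 × 0.837 = 1.64, about 90%, and 1.96 × 1.32 = 2.59, about 99%.

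**Simulation of the code as written.** 20 per arm, normal errors, t interval on 80 − 5 = 75 df, at least 4,000 data sets in the main settings. Equal SDs come first, to reproduce the nominal 95%. All other SD ratios are assumptions. Results are given as vs IR / vs cholecalciferol / vs paricalcitol arm. Coverage is rounded to whole percentages, and repeat runs differed by about one point at most.

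| SDs | v̄ | SE ratio | Coverage, % |
|---|---|---|---|
| 1:1:1:1 | 1.00 | 1.00 / 1.00 / 1.00 | 95 / 95 / 95 |
| 1:1.4:1:1 | 1.24 | 0.92 / 1.11 / 1.11 | 93 / 97 / 97 |
| 1:2:1:1 | 1.75 | 0.84 / 1.32 / 1.32 | 89 / 99 / 99 |
| 1:4:1:1 | 4.75 | 0.75 / 2.18 / 2.18 | 85 / 100 / 100 |
| 2:1:1:1 | 1.75 | 0.84 / 0.84 / 0.84 | 90 / 90 / 90 |
| 2:2:2:1 | 3.25 | 0.90 / 0.90 / 1.14 | 92 / 92 / 97 |
| 1:2:2:1 | 2.50 | 1.00 / 1.00 / 1.58 | 95 / 95 / 100 |
| 1:3:3:1 | 5.00 | 1.00 / 1.00 / 2.24 | 95 / 95 / 100 |

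**With one residual variance per arm** (iterated estimates, Satterthwaite-type df), coverage was 94.4 to 95.6% for every contrast in the settings run. For 1:2:1:1 the mean widths, in units of the smaller SD, were 2.04 for CTAP101 vs IR and 1.28 for the other two, against 1.67 for all three under the SAP code.

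**Is unequal variance plausible?** For Day 1, yes, by inference.
- Dosing is fasted: "Subjects will report to the phase 1 unit on the mornings of Day 1 and Day 29 after an overnight fast" (Protocol 5.5.2).
- For CTAP101, "the current formulation has a BA of approximately 25% when administered in the fasting state" (Protocol 1.9), so 60 × 0.25 = 15 mcg. The IR label (Protocol Appendix 2, section 5.2) puts absorption at 75–80%, so 266 × 0.75 to 266 × 0.80 = 199.5 to 212.8 mcg. The ratio is 13.3 to 14.2, but it divides two different kinds of measure.
- The swine comparison (Protocol 1.8.1), with CTAP101 "approximately 30% lower than that from an IR capsule preparation", gives 266/(60 × 0.70) = 6.3.
- For IR calcifediol, "the time in which the maximum serum concentration is reached is approximately 4 hours", so its peak falls inside the first 24 hours. For cholecalciferol, the 800 IU label (Protocol Appendix 4, section 5.2) says "the maximum serum concentrations of the primary storage form are reached after approximately 7 days". If that carries over to 300,000 IU, little of that arm's response falls in the first day.

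These are ratios of input, not of SD. They would imply a larger Day 1 spread under IR if spread rises with the mean increment, with assay and between-subject noise reducing the contrast.

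For Day 29 the direction cannot be told. CTAP101 has had 28 daily doses, while IR has a new dose plus carry-over from a half-life of 18 to 21 days (Appendix 2).

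**Observed versus baseline-adjusted.** If the subtracted baseline is also the covariate, observed and baseline-adjusted Cmax give identical contrasts and intervals, so the point applies to both.

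**The case against.** The case for leaving the plan alone is substantial. The study is descriptive, the comparison is labelled exploratory, and its parameters are optional. A common-variance ANCOVA is a conventional reading of the ANOVA in Protocol 9.8. Text and code name the same two terms, so the wrong label makes nothing ambiguous. SAP 7.2 reports SD and CV% by treatment and lists every value, so a reader could spot unequal spread and compute a separate-variance interval. Alternative analyses are already permitted. Most of this stands, and it is why the importance is low. What it does not do is correct the intervals and P values that will be printed. The permissive clause names no trigger and no method, so any switch could follow sight of the results.

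A reader might infer that every contrast involving a more variable arm is too narrow. That is not so: under 1:2:2:1 and 1:3:3:1 both CTAP101-vs-bolus intervals are nominal, and only the paricalcitol contrast is off, on the wide side. A reader might also take the 6- to 14-fold input gap as evidence of a given loss of coverage. The documents do not support that. They contain no SDs, and any coverage figure depends on assumed variability and noise more than on the gap.

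**Conclusion.** The mislabelling and the single pooled variance are certain from SAP 7.3. Miscalibration is conditional: it needs unequal variances in a pattern where a contrast's two arms differ, on average, from all four. In the patterns tried, coverage of individual contrasts ran from about 85% to 100%; these figures rest on assumed SD ratios, normal errors and 20 per arm. Unequal variance is plausible for Day 1 Cmax and AUC0-24h. For the three Day 29 parameters neither size nor direction can be stated, so the documents do not support saying that those intervals are too narrow.

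No main conclusion of the study is at stake, and a very large Day 1 difference between CTAP101 and IR would survive either analysis. This is an inexpensive improvement to consider, not a flaw that undermines the study.

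**What to change.** Before database lock, by the amendment route in SAP section 1:
- Add `REPEATED / GROUP=trtp` to the PROC MIXED code, and `DDFM=KR` (or Satterthwaite) to the MODEL statement.
- Rename the model an ANCOVA with arm-specific residual variances.
- Replace the open-ended clause with one named fallback if the model does not converge: separate-variance (Welch) contrasts on the baseline-adjusted parameter. In simulation this gave 95.3% and 94.7% coverage for CTAP101 vs IR with the IR SD at 2 and 4 times the others.

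A log-scale analysis of observed Cmax and AUC may be added. It cannot serve for baseline-adjusted values, because SAP 5.5 and 7.1 retain negative ones.

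The cost is one statement, one option and matching text, with no new data. If the variances are in fact equal, intervals widen by about 1% (1/0.986 = 1.014). The remedy is not perfect. With strongly skewed increments (lognormal, assumed CV 60%, noise SD 10% of the mean IR increment), arm-specific coverage for CTAP101 vs IR was still only about 92 to 94%, against 82 to 83% pooled. The simulations used Satterthwaite-type degrees of freedom, not the SAS Kenward-Roger option itself.

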## 9 SAFETY ANALYSIS

### 9.1 Adverse Events

Adverse events will be coded using MedDRA (Version 21.0 or higher). Each verbatim term will be mapped to a SOC and PT. Severity grades for safety parameters will be assigned using the Common Terminology Criteria for Adverse Events (Version 5.0). When changes in the severity of an AE occur more frequently than once a day, the maximum severity for the experience that day will be noted.

Treatment-emergent AEs (TEAE) are events with onset dates and times on or after the administration of the first dose of study drug and within 30 days after the last dose of study drug, or a continuing AE diagnosed before the date of the first dose of study drug, which increases in frequency, severity, or character during the course of the study.

An overall summary of TEAEs will be provided for the safety population summarizing subjects with at least 1: TEAE, related TEAE, grade 3, 4, or 5 TEAE, serious TEAE, related serious TEAE, TEAE leading to study discontinuation, or related TEAE leading to study discontinuation as well as the number of events within each of the previously mentioned categories by treatment.

In addition, summaries of unique TEAEs will be presented for the safety population by SOC, PT, and by treatment and overall, and will include the number and percentage of subjects who experience the unique event for:

1. All TEAEs,
2. All TEAEs by relationship,
3. All TEAEs by severity grade,
4. All TEAEs leading to study discontinuation,
5. All serious TEAEs, if more than 1 serious TEAE is recorded.

Related TEAEs include all those classified by the investigator as possibly related or related. Unrelated TEAEs are those events classified as not related or unlikely related.

For summaries by relationship, the most related event will be selected. For summaries by severity, the most severe grade will be selected.

Multiple events will be counted only once per subject and treatment in each of the previously mentioned summaries by treatment and overall. In the presentation, SOC and PT will be sorted in alphabetical order.

All AEs captured in the database will be presented in by-subject data listings; however, only TEAEs will be summarized.

MedDRA version will be provided in a footnote in both tables and data listings.

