3.3 Study Duration

This study is expected to be conducted in approximately 26 weeks from time of initial subject enrollment (first subject consented) to study completion for the last subject (last subject out/last visit complete). Subjects will participate in the study for up to approximately 14 weeks (1 week for screening, 4 weeks for washout (if required), 1 week for BL, and 8 weeks for treatment).

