6.6.3 AE Collection Period

All AEs that occur after the ICF has been signed must be reported in detail in the source document and in the appropriate eCRFs and followed to a satisfactory resolution, until the Investigator deems the event to be chronic or the subject to be stable, or until the subject's participation in the study ends.

Information to be collected includes description of the event (event term), date of onset, date of resolution, Investigator-specified assessment of severity and relationship to the investigational study drug, seriousness, as well as any required treatment or evaluations and outcome.

AEs resulting from concurrent illnesses, reactions to concurrent illnesses, reactions to concurrent medications, or progression of disease states must be documented as AEs. Pre-existing conditions (present before the start of the AE collection period) are considered concurrent medical conditions and should NOT be recorded as AEs, but must be documented in the medical history section of the eCRF and in the source document. However, if the subject experiences a clinically significant worsening or complication of such a concurrent condition, the worsening or complication should be recorded as an AE. Investigators should ensure that the AE term recorded captures the change in the condition.

Each AE should be recorded to represent a single diagnosis. Accompanying signs (including abnormal laboratory values) or symptoms should NOT be recorded as additional AEs. If a diagnosis is unknown, sign(s) or symptom(s) should be recorded as an AE(s). Changes in laboratory values are only considered to be AEs if they are judged to be clinically significant (ie, if some action or intervention is required or if the Investigator judges the change to be beyond the range of normal physiological fluctuation). If abnormal laboratory values are the result of pathology for which there is an overall diagnosis (e.g., increased liver enzymes in hepatitis), the diagnosis only should be reported as an AE.

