Pre-planned procedures (surgeries or therapies) that were scheduled prior to the start of AE collection are not considered AEs. However, if a pre-planned procedure is performed early (e.g., as an emergency) due to a worsening of the preexisting condition, the worsening of the condition should be captured as an AE. Elective procedures performed where there is no change in the subject's medical condition (including thought processes around the reason for the elective procedure) should not be recorded as AEs, but should be documented in the subject's source document and captured in the source documentation and eCRF as procedures.

Any report of pregnancy identified for any female subject or for a female partner of a male subject should be reported immediately (within 24 hours of being informed) to the medical monitor. Pregnancies will be considered 'events of special interest' and will not be captured as serious adverse events (SAEs). The Pregnancy Report Form will be utilized to obtain BL and follow-up information. Pregnancies will be followed to termination or six weeks post-delivery

for determination of resolution to the event. Subjects who become pregnant during treatment must immediately be withdrawn from the study (classified as ET).

The Medical Dictionary for Regulatory Activities (MedDRA), Version 20.0 or later, will be used to code all AEs.

6.6.4 *Severity*

The intensity of the AE will be rated by the Investigator per Common Terminology Criteria for Adverse Events (CTCAE) version 5.0.

It should be noted that the clinical severity and seriousness of an AE are not synonymous, e.g., a severe headache is not classified as serious until it meets the required elements as an SAE.

The maximum severity attained for each AE reported will be recorded in the source documentation and in the appropriate eCRFs.

6.6.5 *Relationship*

The Investigator's assessment of an AE's relationship to the investigational study drug is not a factor in determining whether the AE is reported in the source documentation and the appropriate section of the eCRF. If there is any doubt as to whether a clinical observation is an AE, the event should be reported.

The relationship or association of the study drugs in causing or contributing to the AE will be characterized by the Investigator using the classifications and criteria outlined in [Table 3](#).

Table 3 Adverse Event Relationship Criteria

Relationship	Criteria

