6.6.8 Treatment-Emergent Adverse Events

A TEAE is defined as any AE with onset or worsening reported by a subject from the time that the first dose of study drug is taken in this study until 30 days following discontinuation of study drug administration.

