7 STUDY ACTIVITIES

7.1 Screening Period

7.1.1 *Visit 1 (Days -70 or -42 to -36)*

- A signed ICF will be obtained from the subject prior to any study-related procedures
- Review of inclusion/exclusion criteria
- Medical history and demographics
- Review of prior and current medications
- PE (including weight, height and BMI)
- VS assessment
- Serum pregnancy test (for females of child bearing potential)
- Serum hepatitis B and C/HIV screen
- Drugs of abuse screen
- eGFR
- Urinary albumin excretion
- Blood samples will be drawn for the following:
 - Clinical chemistry (full panel) and hematology
CCI [REDACTED]
- Dietary questionnaire for calcium intake and counseling, if needed.

If the screening values do not meet study entry criteria after visit 1, subject may receive supportive care per the investigator's discretion and may be retested once. If values do not fall within study entry criteria on retest, the subject will be considered a screen failure and be withdrawn from the study. Only the screening values that did not meet entry criteria at visit 1 are required to be re-drawn and meet entry criteria at the time of the visit 1 retest.

7.1.2 *Visits 2 and 3 (Within Days -7 to -1)*

- Review of inclusion/exclusion criteria
- Review of concomitant medications
- AE assessment
- VS assessment
- Serum pregnancy test (for females of child bearing potential) (Visit 2 only)
- Blood samples will be drawn for the following:
 - Clinical chemistry (full panel) and hematology
CCI [REDACTED]
- Blood samples will be drawn for:
 - CCI [REDACTED] calcifediol, and CCI [REDACTED]
CCI [REDACTED]

CC1

- [REDACTED]
- Subjects will be instructed to report to the phase 1 unit for Visit 4 after an overnight fast.

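### SAP 9.1 does not tie worsening of a pre-dose adverse event to the first dose, so its TEAE rule is wider than the one in Protocol 6.6.8

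*SAP*

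**What the plan says.** **TEAE definition in the protocol.** Section 6.6.8 defines a TEAE as "any AE with onset or worsening reported by a subject from the time that the first dose of study drug is taken", with the window closing 30 days after study drug is discontinued. Onset and worsening share that window.

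**TEAE definition in the SAP.** Section 9.1 has two branches. A new-onset event must start between the first dose and 30 days after the last dose. The second branch reads "or a continuing AE diagnosed before the date of the first dose of study drug", and continues "which increases in frequency, severity, or character during the course of the study". It carries neither the first-dose start nor the 30-day end.

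**When AEs are collected.** Protocol 6.6.3: "All AEs that occur after the ICF has been signed must be reported in detail". Visit 1 falls at Day -70 or between Days -42 and -36 (Protocol 7.1.1). AEs are also assessed at Visits 2 and 3, before the first dose on Day 1.

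**How severity and worsening are recorded.** Protocol 6.6.4: "The maximum severity attained for each AE reported will be recorded in the source documentation and in the appropriate eCRFs". SAP 9.1 says that when severity changes more than once a day, "the maximum severity for the experience that day will be noted". Protocol 6.6.3 has a clinically significant worsening of a condition present before AE collection entered as an AE of its own. It gives no matching rule for an AE that starts between consent and first dose.

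**The concern.** The two documents give different rules for the same status. In the SAP sentence the dosing window is attached to new onset but missing from worsening. Because AE records begin at consent, a change that took place wholly before any study drug can satisfy the SAP wording.

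TEAE status decides what is tabulated. AEs are part of the primary safety endpoints (Protocol 2.2.3), and SAP 9.1 summarizes only TEAEs and leaves other AEs to the listings. An event that worsened only before dosing would appear in the summary tables under the assigned treatment.

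There is a second, conditional issue. Even a corrected definition needs a date for the worsening, and the documents do not agree on whether one is captured.

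**Working it through.** The documents give no TEAE rate, expected count or calculation for this point, so there is no figure to reproduce. The check compares the two definitions and then sizes one misclassified subject.

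**Step 1. Classify every history of an AE that began after consent and is ongoing at first dose.** The SAP is read literally, with the study taken to start at consent. Worsening after dosing is taken to fall within 30 days of the last dose.

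| Worsened before first dose | Worsened after first dose | SAP 9.1, literal | Protocol 6.6.8 |
|---|---|---|---|
| No | No | not a TEAE | not a TEAE |
| No | Yes | TEAE | TEAE |
| Yes | No | **TEAE** | **not a TEAE** |
| Yes | Yes | TEAE | TEAE |

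One history of four differs. In that row the SAP counts an event that the protocol does not, so the literal wording can only over-count.

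**Step 2. Does the missing 30-day end matter?** For subjects who keep to schedule it does not. A monthly-arm subject dosed on Day 29 has a window to Day 29 + 30 = 59. A daily-arm subject dosed for 56 days has a window to Day 56 + 30 = 86. Both lie beyond the last visit on Day 57. The end can matter only for a subject whose dosing stops early, and the same correction covers that case.

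**Step 3. Can pre-dose worsening be recorded at all?** Yes. With Visit 1 at Day -70 or Days -42 to -36, there are 36 to 70 days of AE collection before the first dose.

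**Step 4. Size of one misclassified subject.**

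- In an arm of about 20: 1/20 = 5.0 percentage points.
- Over all of about 80: 1/80 = 1.25 percentage points.

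This applies to a preferred-term row if the subject has no other TEAE with that term. It applies to the any-TEAE row only if the subject has no other TEAE.

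**Step 5. Can the corrected rule be applied to the data?** Protocol 6.6.2 to 6.6.4 name onset, resolution, duration, description, maximum severity, relationship, action, outcome and seriousness. None is a date of worsening. Take an AE that starts on Day -30 at grade 1. In one subject it reaches grade 2 on Day -15 and stays there; in another it reaches grade 2 on Day 20. If onset date and a single maximum grade were all that was kept, the two records would look alike in those fields. The SAP's daily-maximum sentence, on the other hand, presupposes dated severity changes. The documents conflict here, and the eCRF is not among them.

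**The case against.** The strongest reply is that the SAP clause is ambiguous rather than wrong. SAP 2.2.2 and 7.2 treat the 56 treatment days as the whole study period, and SAP 3.3 places the Day 1 stay at the beginning of the study. On that usage the clause already means worsening after dosing and agrees with the protocol. Protocol 3.3, however, counts screening, washout and baseline within study participation of up to about 14 weeks. Both usages are present, so the SAP does not settle the rule for the person programming it. The reply softens the point but does not remove it.

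The reply on consequences is sound. Randomization takes place at Visit 4, after any pre-dose worsening, so no arm should gain or lose in expectation. Safety summaries are descriptive (Protocol 9.10), all AEs are listed, and relationship is rated separately, with timing relative to administration among its criteria. A TEAE can still be rated not related.

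On data capture, a reader might infer from Protocol 6.6.4 that pre-dose and on-drug worsening cannot be told apart. The documents do not show this. Section 6.6.4 requires the maximum severity but does not say that nothing else is kept, AEs are assessed at visits before and after dosing, and the eCRF and its completion instructions are not available. What stands is that no provision for dating such a worsening is described.

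**Conclusion.** The discrepancy is real and narrow. Read literally, SAP 9.1 makes a TEAE of an AE that began after consent, worsened only before first dose and was still ongoing at dosing; Protocol 6.6.8 does not. The effect is over-counting and noise in descriptive tables, at 5 percentage points per affected subject for a given term in an arm of about 20. How many subjects will be affected is unknown and may be none. The conclusion assumes that the course of the study includes the pre-dose period, as Protocol 3.3 allows.

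Three stronger readings go beyond the documents:

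- *TEAE counts are wrong for all AEs ongoing at first dose.* Within the dosing window, three of the four histories get the same status under both rules.
- *The share of calendar time before dosing gives the share of worsenings misclassified.* An AE can worsen only after it has started, so its time at risk begins at its onset and not at consent. The documents give no worsening rate.
- *Prolonged withdrawal of active vitamin D therapy makes pre-dose worsening common.* Washout applies only if required. Inclusion criterion 4d sets four weeks for calcitriol and 1α-hydroxylated analogs. The extension to eight weeks in criterion 4e concerns vitamin D supplements.

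**What to change.** **SAP 9.1.** Replace the worsening branch with wording such as: an AE with onset before the first dose that increases in severity, frequency or character on or after the first dose and within 30 days after the last dose. This matches Protocol 6.6.8.

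**Recording.** So that the rule can be applied, reconcile the per-AE maximum severity in Protocol 6.6.4 with the SAP's daily-maximum sentence. Extend the Protocol 6.6.3 rule on entering a worsening as its own AE to AEs that start between consent and first dose. Either of two conventions would serve:

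- a new record for the worsening, with its own onset date, grade and relationship; or
- dated severity changes within the existing record.

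If the eCRF already does one of these, it is enough to say so and to name the field used for the TEAE flag. A dated change in severity alone does not cover frequency or character, so the second option needs a date for those as well.

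**Cost.** One SAP sentence, amended before database lock, and one recording rule. Under the new-record option a few AE rows are added, so event counts rise slightly. Visits and treatment do not change.
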